**Trial #: NCT02487251**

**Protocols and Analytic Plans**

**Originally Submitted: 7/14/21**

**Updated: 9/27/21**

## **Phase 1 Study Protocol**

In a factorial design with six intervention components reflecting supports for family mealtimes (e.g., meal delivery, cookware/dinnerware provision, nutrition education, etc.), individual participants were randomized to one of 64 experimental conditions. The 64 experimental conditions result from the crossing of six interventions, each of which had two conditions (present vs. not) and reflect all possible pairings of the intervention components including a condition with no intervention components. Feasibility was assessed via attendance/participation in intervention components. The intervention period was 8 weeks.

Families were recruited from two Head Start agencies serving a mix of rural and urban areas in mid-Michigan. Participants were recruited on-site at their children's Head Start programs during parent events or through informational packets that were sent home in children's backpacks. Parents expressing an interest in study participation were screened for eligibility. Written consent was obtained from all participants during a home visit. Families were assigned to study interventions through an automated random number generator.

Data collection teams were distinct from the intervention staff and were managed separately. Evaluators of study outcomes were blinded to the intervention components to which participants were assigned. After obtaining written informed consent and prior to starting the intervention, a data collector made a home visit to measure maternal and child weight and height and complete a series of questionnaires with the mother. Following the implementation of the intervention, a parallel post-intervention data collection visit was conducted.

## **Phase 2 Study Protocol**

Families were enrolled, consented and randomly assigned to the intervention or to usual care control group. Outcome measures were collected both pre- and post-intervention while data on dietary quality were also collected mid-intervention. Most data were collected in the home; however, with the onset of the global COVID-19 pandemic, data collection was moved to an online platform through which participants completed self-reported questionnaires. Because in-person data collection efforts were not possible, measurements of child height/weight and data on mealtime interactions were not collected for participants with data collection points falling after March 2020. Families received written and verbal information about the study and provided written informed consent. Data collectors and interventionists did not interact, and data collectors were blinded. Participants in the intervention condition received two meals per week for 12 weeks and they received a comprehensive set of cookware/dinnerware at the outset of the intervention delivery.

### **Phase 1 Analytic Plan**

The results of the six intervention components were identified by means of a factorial experiment involving the following factors: 1) Meal Delivery (provided vs. not); 2) Ingredient Delivery (provided vs. not); 3) Community Kitchen (provided vs. not); 4) Didactic Nutrition Education Classes (provided vs. not); 5) Cooking Lessons (provided vs. not); and 6) Cookware/Materials Provision (provided vs. not). Pre- to post-intervention change scores were calculated for each intervention condition. Using Cohen's  $d$  to assess effect sizes of pre-post changes for each primary and secondary outcome, results were categorized using the following a priori thresholds for interpretation and compared to the control condition: small ( $d \leq .30$ ), medium ( $d > .31$  and  $\leq .50$ ), and large ( $d \geq .80$ ). This emphasis was consistent with our objective of identifying a feasible, final set of bundled components. Then, paired t-tests were conducted to

examine pre- to post-intervention changes within the intervention combinations that included Meal Delivery and Cookware/Materials Provision (N = 65), identified as the two most feasible, and promising intervention components. Because sample sizes within each of the intervention combinations were small and because participation in all interventions except Meal Delivery, Ingredient Delivery and Cookware/Materials provisions was so negligible (described in the results), we elected to use combined samples in the paired t-tests analyses. Thus, the 65 participants received Meal Delivery and Cookware/Materials Provision but may have also received other interventions except for Ingredient Delivery. The rationale for this was that the extremely low participation in Community Kitchen, Nutrition Education, and Cooking Demonstrations would result in no intervention effects related specifically to these intervention components. As a caution, we also examined pre-post analyses with the small group of participants who only received Meal Delivery and Cookware/Materials Provision.

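### Phase 1 effect sizes set raw pre-post change against control without adjusting for the baseline already collected, which loses some precision and lets chance baseline gaps move some labels

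*Combined protocol and SAP*

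**What the plan says.** The Phase 1 Analytic Plan states that "Pre- to post-intervention change scores were calculated for each intervention condition". It uses Cohen's d "to assess effect sizes of pre-post changes for each primary and secondary outcome", and then "results were categorized using the following a priori thresholds for interpretation and compared to the control condition". The SD that forms the denominator of d is not stated, and no model or test is given for the comparison with control. Neither regression nor a baseline covariate is described for Phase 1. Mixed models and covariates appear only in the Phase 2 Analytic Plan.

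The baseline is available. According to the Phase 1 Study Protocol, before any component was delivered "a data collector made a home visit to measure maternal and child weight and height and complete a series of questionnaires with the mother". Afterwards, "a parallel post-intervention data collection visit was conducted".

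**The concern.** A change score fixes the coefficient of baseline at 1. Where the pre-post correlation is below 1, this over-corrects: a condition that starts low by chance tends to rise more than control even if the intervention does nothing. Regressing the post value on the pre value estimates the coefficient from the data and removes that part of the error.

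This matters more when groups are small. Phase 1 spreads families over many combinations, and the plan itself calls the samples within combinations small. Its effect-size labels were one input to the choice of Meal Delivery and Cookware/Materials Provision, the two components that Phase 2 then delivered.

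**Working it through.** **Inputs from the documents.** In Phase 1, "individual participants were randomized to one of 64 experimental conditions", which matches six two-level components (2^6 = 64). The pooled paired analysis has 65 participants, who "received Meal Delivery and Cookware/Materials Provision but may have also received other interventions except for Ingredient Delivery". Two components are therefore fixed as present, one is fixed as absent and three are free. That gives 2^3 = 8 combinations, and 65/8 = 8.1 families in each if they are evenly spread.

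**Assumptions.** Pre and post SDs are equal. The pre-post correlation r is taken as 0.3, 0.5, 0.7 or 0.9. Each cell has n = 8, including the no-component control, whose size is not given.

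**The plan's own figure.** Phase 1 states no total sample size, power or alpha, so there is no Phase 1 calculation to reproduce. The Phase 2 figure of 125 per arm does reproduce (99 per arm for d = 0.40, and 99/0.80 = 123.75, so 124), but it has no bearing on this point.

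**Step 1: precision of one condition against control, in outcome-SD units.**

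- Change score: variance = 2 × 2(1-r)/n
- Baseline-adjusted: variance = 2 × (1-r²)/n
- Ratio, adjusted to change score: (1-r²)/[2(1-r)] = (1+r)/2

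| r | SE, change score | SE, adjusted | Variance ratio | Extra families a change score needs | Narrower interval |
|---|---|---|---|---|---|
| 0.3 | 0.592 | 0.477 | 0.65 | 54% | 19% |
| 0.5 | 0.500 | 0.433 | 0.75 | 33% | 13% |
| 0.7 | 0.387 | 0.357 | 0.85 | 18% | 8% |
| 0.9 | 0.224 | 0.218 | 0.95 | 5% | 3% |

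Extra families = 1/ratio - 1. Reduction in interval width = 1 - sqrt(ratio).

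**Step 2: the part due to chance baseline gaps.** The gap between two cells of 8 has SD sqrt(2/8) = 0.50, and the change score carries (1-r) of it. In change-SD units this is divided by sqrt(2(1-r)). Its share of the contrast's variance is (1-r)/2.

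| r | SD, outcome units | Beyond ±0.30 | SD, change-SD units | Beyond ±0.30 | Share of variance |
|---|---|---|---|---|---|
| 0.3 | 0.35 | 39% | 0.30 | 31% | 35% |
| 0.5 | 0.25 | 23% | 0.25 | 23% | 25% |
| 0.7 | 0.15 | 5% | 0.19 | 12% | 15% |
| 0.9 | 0.05 | about 0% | 0.11 | under 1% | 5% |

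Both scales are shown because the plan does not define the denominator of d. The medium band runs from .31 to .50, a width of 0.19, so a baseline gap of ordinary size can move a label unless r is high.

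**Step 3: total label noise before and after adjustment.** Suppose there is no true effect, and work in change-SD units. The change-score contrast has SE 0.50 at every r, so P(d > .30) = P(Z > 0.60) = 27%. After adjustment the SE is 0.50 × sqrt((1+r)/2), and the probability is 23%, 24%, 26% and 27% at the four values of r. In a simulation of 200,000 null contrasts, the two methods disagreed on whether d exceeded .30 in 16%, 14%, 11% and 6% of cases.

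**Step 4: where the slope is estimated.** If the adjusted model is fitted to one pair of 8-family cells, its variance is inflated by about 1 + 1/(2×8-4) = 1 + 1/12. The ratios become 0.70, 0.81, 0.92 and 1.03, so at r = 0.9 the gain is gone. One common slope estimated across all cells avoids this.

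**The case against.** Four counter-arguments have force.

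- **The contrast is not clearly defined.** The plan's d reads as a within-condition effect that is labelled and then compared descriptively with control. The variance ratio applies to a between-group contrast. This stands, and the fix must therefore define such a contrast as well as add a covariate.
- **The size is uncertain.** r is not given, 8 per cell is inferred, and the units of d are unstated. Weight and height over an 8-week intervention may have a high r (an assumption), in which case the saving is about 5% of variance. This also stands.
- **Selection did not rest on effect sizes alone.** Feasibility was judged by attendance and participation, and the plan calls participation in three of the six components negligible. A reader might infer that every Phase 1 result depends on change scores. The documents do not support that, because the point covers only the outcome effect sizes.
- **The timing limits the consequence.** The documents are written in the past tense and Phase 2 has been delivered. A re-run can improve the Phase 1 report but cannot alter what entered Phase 2.

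None of these gives a reason to leave out a baseline that has already been measured. They limit the size of the point and shape the remedy.

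**Conclusion.** The point holds as a moderate, inexpensive improvement. Raw change is an unbiased but less efficient basis for comparing randomised conditions. Under the stated assumptions, adjustment reduces the variance by 35%, 25%, 15% or 5% at r = 0.3, 0.5, 0.7 or 0.9, and it removes the component due to chance baseline gaps.

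Two stronger readings are tempting and should be resisted. A reader might infer that baseline gaps drive the labels. They do not: under no effect, the chance of d above .30 falls only from 27% to between 23% and 27%, because cells of about 8 dominate the noise. A reader might also infer that change scores bias the results, or that adjustment narrows every comparison. Randomisation protects against bias on average, and the gain can vanish for very stable measures if the slope is estimated from a single pair of cells.

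**What to change.** For each outcome, fit one linear model across all randomised families: the post value on the six component indicators plus the pre value of the same outcome, with a single baseline slope. Apply the labels to the adjusted between-group difference divided by the baseline SD, which also settles the denominator of d. State that the comparison is component present against absent, and that without interaction terms the component effects are assumed to add. Keep raw within-condition change, including the paired analysis of the 65, as descriptive only.

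The cost is revised analysis wording, a re-run on data already held, and one degree of freedom per outcome for the baseline term. The gain will be small for highly stable measures. The feasibility assessment by attendance is unaffected.

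### Phase 1 appears to class Cohen's d cell by cell against a single control cell and describes no factorial main-effect contrast, so with small cells many labels of medium or larger could be chance

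*Combined protocol and SAP*

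**What the plan says.** The Phase 1 Study Protocol describes a full crossing of six present-or-absent components, in which "individual participants were randomized to one of 64 experimental conditions". The cells cover "all possible pairings of the intervention components including a condition with no intervention components". The same section also speaks of each component as having two conditions, present or not.

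The Phase 1 Analytic Plan lists the six factors and then says that "Pre- to post-intervention change scores were calculated for each intervention condition". Cohen's d of pre-post change is sorted into small, medium (above .31 up to .50) and large (.80 or more) for every primary and secondary outcome, using "a priori thresholds for interpretation and compared to the control condition". How that comparison is made, and which SD scales d, is not stated.

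Only after this step does the plan pool cells. It runs paired t-tests on 65 families who had Meal Delivery and Cookware/Materials Provision and who "may have also received other interventions except for Ingredient Delivery". One reason given is that "sample sizes within each of the intervention combinations were small". A further check uses the small group with those two components alone. The section describes no main-effect or interaction model, no confidence interval for d and no multiplicity rule. The documents give neither the Phase 1 total nor any cell size.

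**The concern.** A 2^6 factorial is efficient because every family contributes to the estimate of every component: half the sample has the component and half does not. Comparing one cell with one control cell uses 2 of the 64 cells and discards that advantage. A d computed from a handful of families varies so widely that fixed bands mostly sort sampling noise, and the sorting is repeated over many cells and outcomes.

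The pooled paired t-tests do not fill the gap. They test change within one group with no named comparator, so they cannot separate an intervention effect from maturation, season or regression to the mean.

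The plan links the effect-size step to finding a feasible final bundle and calls the two chosen components promising as well as feasible. What is at stake is how far Phase 1 supports the word promising.

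**Working it through.** The plan gives no Phase 1 sample-size or power figure to reproduce. The check starts from its counts.

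**Inputs**
- Cells: 2^6 = 64, of which 1 has no components and 63 are active (Phase 1 Study Protocol).
- Pooled families: 65, with Meal Delivery and Cookware on and Ingredient Delivery off (Phase 1 Analytic Plan).
- Thresholds: .31, .50 and .80 (Phase 1 Analytic Plan).
- Assumption: about equal allocation across cells.

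**Cell size.** Three factors are free among the 65, so they span 2^3 = 8 cells, and 65/8 = 8.1 per cell. Carried to all 64 cells, this implies 64 × 65/8 = 520 families.

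**Chance rate, within-cell d.** With no true change and d scaled by the SD of change, d = t/√n on n − 1 degrees of freedom, so P(d > .31) = P(t > .31√n). At n = 8, .31√8 = 0.877 on 7 df, which gives 0.205 (simulation 0.203). This divides as follows:

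| d in the favourable direction | Probability at n = 8 |
|---|---|
| .31 to .50 (medium) | 0.105 |
| .50 to .80 (no label in the plan) | 0.071 |
| .80 or more (large) | 0.029 |
| Total above .31 | 0.205 |

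If all 63 active cells were this size, the expected counts per outcome would be 63 × 0.205 = 12.9 above .31 and 63 × 0.029 = 1.8 at .80 or more.

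**Sensitivity of the 0.205**
- Cell size: 0.24 at n = 6, 0.18 at n = 10, 0.15 at n = 12.
- Baseline SD as the scale: P(Z > .31√n / √(2(1 − r))), a normal approximation. At n = 8 this is 0.19, 0.13 and 0.08 for pre-post correlation r = 0.5, 0.7 and 0.8.

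**Chance rate, d against the control cell.** With n families in each cell, P(d > .31) = P(t > .31√(n/2)) on 2n − 2 df. At n = 8, .31 × 2 = 0.62 on 14 df, which gives 0.273.

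**Precision, in SD units of change**
- Cell versus control cell: SE = √(2/n) = √(2/8) = 0.50.
- Main effect: SE = 2/√(64n). With the implied total, 2/√520 = 0.088.
- Ratio: √(2/n) ÷ (2/√(64n)) = √2 × 8/2 = 5.66 for any n, a 32-fold difference in variance.
- Power at d = 0.31, two-sided .05, normal approximation: 9% for 8 versus 8, and 94% for 260 versus 260.
- Chance of a main-effect estimate above .31 with no true effect: P(Z > .31/0.088), about 0.0002.

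**The case against.** **The unit may be the component level.** The change-score sentence directly follows a list of six factors, each provided or not, and the Phase 1 Study Protocol uses the word in that sense too. If d was computed by factor level, the chance rate is negligible. This stands as a reason to ask for the unit to be stated. Against it, the plan names a single control condition, which matches the one no-component cell; a factor-level analysis would have six absent-level comparators. Combining samples is mentioned only for the t-tests. The remark on small combinations explains that later pooling, so it is weaker evidence about the d step.

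**One in five does not land in the medium band.** A reader might infer that it does. The 20% is for medium or larger; about 10% falls inside .31 to .50. It also applies to an uncontrolled within-cell d. The figure against the control cell is 27%, and the two should not be mixed.

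**About 8 per cell is inferred.** The documents mention an automated random number generator but state no blocking, and the 65 are described as having received the components, which may not equal the number randomized. The counts out of 63 and the 0.088 rest on the assumption. The 5.7-fold ratio needs equal allocation but no particular cell size.

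**The authors saw the problem and pooled.** They did, so it would be too strong to say that the design's information went wholly unused. But pooling 8 cells for a test without a comparator does not give a randomized contrast.

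**Feasibility drove selection.** Attendance was the feasibility measure, and participation in three components was very low. The weight given to d is not stated, and the chosen package was then tested in a randomized Phase 2. This stands and limits the consequence.

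**Conclusion.** The concern holds as a weakness in how Phase 1 estimates component effects. On the more natural reading, d is classed by cell against one control cell. On either reading, no factorial main-effect contrast is described, and the unit, comparator and scaling SD of d are left open.

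Assuming about equal allocation and 8 families per cell, a within-cell d exceeds .31 in the favourable direction by chance in about 20% of cells per outcome, and about 3% reach .80. The 20% moves between 15% and 24% for cells of 12 down to 6, and falls to 8% if d is scaled by baseline SD with a pre-post correlation of 0.8. Against the control cell it is about 27%. The loss of precision relative to a main effect is 5.7-fold in standard error.

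A reader might go further and infer that noise selected the wrong components for Phase 2. The documents do not support that: feasibility also drove the choice, and nothing shows that the bands alone decided it. Phase 2 has been run, so the point bears on what Phase 1 can conclude about which components are promising.

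**What to change.** State whether d is computed by cell or by component level, against which comparator, and with which SD. Report the number randomized and analysed in each cell.

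For each outcome, fit one regression on all randomized families: the post value on the baseline value, six effect-coded factors and a short list of two-way interactions named in advance of the re-analysis, for example Meal Delivery by Cookware/Materials Provision. Coding each factor as −½ and +½ makes its coefficient the present-minus-absent difference. Report the main effects with 95% confidence intervals, apply the effect-size bands to those estimates rather than to individual cells, and label any cell-level d as descriptive.

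The cost is a re-analysis of data already held and revised wording in the Phase 1 Analytic Plan. No new data are needed. Because the analysis would follow the results, it should be reported as such.

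### Phase 1's only described significance tests are paired pre-post tests in 65 families who all had the bundle, so they cannot separate a bundle effect from background change

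*Combined protocol and SAP*

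**What the plan says.** The Phase 1 Study Protocol crosses six present/absent components into 64 conditions that "reflect all possible pairings of the intervention components including a condition with no intervention components". Families were assigned by a random number generator, with an 8-week intervention and a home visit before and after it.

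The Phase 1 Analytic Plan has three steps:

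- **Effect sizes.** Pre-post change is summarised per condition as Cohen's d, and "results were categorized using the following a priori thresholds for interpretation and compared to the control condition". No test, interval or model is attached to this comparison.
- **Paired tests.** These were run to "examine pre- to post-intervention changes within the intervention combinations that included Meal Delivery and Cookware/Materials Provision (N = 65"; the two components were "identified as the two most feasible, and promising intervention components". On pooling, the plan says that "the 65 participants received Meal Delivery and Cookware/Materials Provision but may have also received other interventions except for Ingredient Delivery".
- **Check.** "As a caution, we also examined pre-post analyses with the small group of participants who only received Meal Delivery and Cookware/Materials Provision".

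No between-group test, factorial model, or adjustment for time or season is described for Phase 1.

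**The concern.** A paired t-test asks whether the mean change in one group differs from zero. When everyone in the group had the bundle, a significant answer is equally compatible with a bundle effect, a common time trend, a repeat-questionnaire effect, or some regression to the mean. The cautionary analysis is also pre-post, in fewer families, and has the same limit.

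Background change is plausible. The Phase 2 Analytic Plan reports seasonal differences in BMIz and dietary measures in its baseline data and adjusts for season. That does not tell us the size of any drift in Phase 1.

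At stake is any Phase 1 statement that the bundle improved an outcome. The randomised design could have tested that directly.

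**Working it through.** The plan gives no derivation for the 65, so there is no figure of its own to reproduce.

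**Inputs.** From the Phase 1 sections: n = 65, paired t-test, 64 cells from six two-level factors. Assumed: two-sided α = 0.05 (stated only for Phase 2); pre-post correlation ρ of 0.3, 0.5 and 0.7; equal SD before and after; background drift of 0.1 or 0.2 SD of the outcome; equal allocation to cells.

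**1. Available comparator.** Meal Delivery and Cookware present with Ingredient Delivery absent fixes three of six factors and leaves 2³ = 8 cells. Having none of the three also leaves 2³ = 8 cells. Both sets cross the same three low-uptake components (Community Kitchen, Nutrition Education, Cooking Lessons), so the plan's reason for pooling applies equally to the comparator. Equal allocation gives 65/8 ≈ 8.1 families per cell, hence about 65 comparators in total but only about 8 in the single no-component cell.

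**2. How often the paired test is significant with no bundle effect.** The standardised change is d_z = drift / √(2(1 − ρ)). The rejection rate comes from a non-central t with 64 df and non-centrality d_z√65.

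| Drift | ρ = 0.3 | ρ = 0.5 | ρ = 0.7 |
|---|---|---|---|
| 0 | 5% | 5% | 5% |
| 0.1 SD | 10.3% | 12.5% | 17.6% |
| 0.2 SD | 26.9% | 35.5% | 53.6% |

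Example: drift 0.2 and ρ = 0.5 give d_z = 0.2/√1 = 0.2, non-centrality 0.2 × 8.06 = 1.61, rejection 35.5%.

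Simulation (5,000 runs per setting, 65 v 65, same drift in both groups) gave 10.3/13.1/18.0% and 27.2/35.0/53.3% for the paired test. ANCOVA between groups rejected 4.8% to 5.5% of the time.

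**3. Whether the descriptive control comparison fills the gap.** The 95% half-width for a difference in mean change, in SD of the outcome, is t × √(2(1 − ρ)) × √(1/n₁ + 1/n₂).

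| Comparison | ρ = 0.3 | ρ = 0.5 | ρ = 0.7 |
|---|---|---|---|
| 65 v 8 | 0.88 | 0.75 | 0.58 |
| 65 v 65 | 0.41 | 0.35 | 0.27 |

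Example: 65 v 8 at ρ = 0.5 gives 1.994 × 1 × 0.375 = 0.75.

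**4. Detectable difference at 80% power.** The paired test at n = 65 detects a change of 0.42, 0.35 and 0.27 SD at ρ = 0.3, 0.5 and 0.7. ANCOVA, with residual SD √(1 − ρ²), detects a difference of 0.47, 0.43 and 0.35 SD for 65 v 65. At ρ = 0.5 with 40, 50 or 80 comparators it detects 0.49, 0.46 or 0.41 SD.

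**The case against.** The strongest case is about importance. Phase 1 aimed to find a feasible bundle, and feasibility was judged on participation. The plan says the paired tests examine change; it does not claim that they estimate a bundle effect. Efficacy is tested in Phase 2 against usual care. This stands, and it limits the consequence to Phase 1 outcome statements. It does not make the test informative about the bundle.

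Other points, and what remains of each:

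- **The drift is assumed.** True. With none, the paired test rejects 5% of the time, and the between-group rate near 5% follows by construction when drift is shared. The table shows sensitivity to drift and does not estimate an error rate for this trial.
- **Regression to the mean needs selection on extreme baseline values, and no such entry criterion is given.** Fair. It is the weakest of the listed explanations; the other two do not depend on it.
- **The plan compares condition by condition, so 65 v 8 is not its comparison, and ANCOVA would be tighter.** ANCOVA would give half-widths of 0.71, 0.65 and 0.53 SD for 65 v 8, still wide. A per-condition comparison of about 8 v 8 would be weaker again.
- **A main-effects factorial model on all families would be more precise.** If about 520 families were analysed (64 × 8 ≈ 512, rounded up from 65/8 per cell), the summed Meal Delivery and Cookware effects have standard error √0.75 × √(8/520) = 0.107 at ρ = 0.5, detectable at about 2.80 × 0.107 = 0.30 SD. That sum equals the bundle contrast only if the components act additively. It is a legitimate trade-off, but it rests on that assumption.
- **That the bundle was chosen before testing, and on the same data, is inferred.** Correct: it is read from the order of the text.

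**Conclusion.** The concern holds. As described, Phase 1's significance tests have no concurrent comparator, and neither the descriptive control comparison nor the cautionary analysis supplies one. A shared drift of 0.1 to 0.2 SD would raise the chance of a significant result with no bundle effect from 5% to between 10% and 54%, given ρ of 0.3 to 0.7 and two-sided 0.05. Those drifts, correlations and the equal cell sizes are assumptions. The qualitative conclusion needs none of them: a within-group test cannot attribute change to the bundle.

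This should be fixed, because the remedy is cheap and the randomised comparator exists. It does not bear on Phase 2's efficacy test.

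**What to change.** Replace the paired test as the Phase 1 inference with wording such as:

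> For each outcome, ANCOVA of the post value on the pre value compares all families randomised to the 8 cells with Meal Delivery and Cookware but no Ingredient Delivery with all families randomised to the 8 cells with none of these three. The difference, its 95% CI and the number analysed per group are reported.

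- Group families by assignment. The plan describes the 65 as having received the components, so state whether they are all the families randomised to those cells.
- An alternative is a factorial model on all randomised families with every two- and three-way interaction among Meal Delivery, Cookware and Ingredient Delivery, taking the same contrast with Ingredient Delivery absent. If a main-effects model is preferred for precision, state the additivity assumption.
- Keep the paired changes as descriptive. Label the contrast exploratory, because the bundle appears to have been judged promising on the same data; neither analysis removes that selection, so a 5% error rate is not guaranteed.

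**Cost.** Re-analysis of data already collected, a few lines of code and revised wording. It cannot change which bundle entered Phase 2. The detectable difference at ρ = 0.5 rises from 0.35 SD to about 0.43 SD with 65 comparators, but the smaller figure is for change from any cause. About 65 comparators is expected only under equal allocation and similar retention, so the actual number must be given.

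### Phase 1 leaves Ingredient Delivery out of the bundle without a reason of its own, and the described analyses cannot reliably compare it with Meal Delivery

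*Combined protocol and SAP*

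**What the plan says.** The Phase 1 Study Protocol describes a full crossing of six two-level components in which "individual participants were randomized to one of 64 experimental conditions". It gives the feasibility criterion as follows: "Feasibility was assessed via attendance/participation in intervention components".

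The Phase 1 Analytic Plan lists Ingredient Delivery as a factor in its own right, separate from Meal Delivery. It describes two kinds of analysis:

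- Change scores by condition, with Cohen's d used "to assess effect sizes of pre-post changes for each primary and secondary outcome". The plan adds that "results were categorized using the following a priori thresholds for interpretation and compared to the control condition".
- Paired t-tests in 65 families who had Meal Delivery and Cookware/Materials, the pair "identified as the two most feasible, and promising intervention components". These families "may have also received other interventions except for Ingredient Delivery". A smaller set who had only those two components is examined as a check.

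The reason given for pooling is that "participation in all interventions except Meal Delivery, Ingredient Delivery and Cookware/Materials provisions was so negligible". The supporting argument then names only the community kitchen, the nutrition classes and the cooking component. The Phase 2 Study Protocol carries forward meals and cookware/dinnerware only.

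**The concern.** Three components escape the negligible-participation label, but only two go forward. The no-effect argument that justifies pooling over the three poorly attended components is not extended to Ingredient Delivery, and nothing else is said about why it was dropped.

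Phase 1 exists to choose the components of the bundle. Two outcome questions bear on that choice: how Meal Delivery compares with Ingredient Delivery, and whether Ingredient Delivery adds anything to Meal Delivery. Both factors were randomised and crossed, so the design can address both questions. No main-effect, interaction or Meal v Ingredient estimate is described. At stake is how strongly Phase 1 can be said to support the Phase 2 bundle on outcomes.

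**Working it through.** **Inputs.** Six two-level factors, 64 conditions and N = 65 come from the two Phase 1 sections. The plan gives no Phase 1 total, participation rate or power statement. The group sizes below therefore assume equal allocation.

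**The plan's own figures.** 2^6 = 64 conditions, as stated. The only sample-size calculation is for Phase 2 and is not in question: 2 x (1.960 + 0.842)^2 / 0.40^2 = 98.1, so 99 per arm. Then 99 / 0.80 = 123.75, or 124, against the stated 125.

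**What each described analysis can say about Ingredient Delivery**

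1. *Paired t-tests in the 65.* No Ingredient Delivery recipient is included and there is no concurrent control. The tests carry no information on Meal v Ingredient or on Ingredient added to Meal. The same is true of the smaller Meal-plus-Cookware-only check.
2. *Condition-level d against control.* Ingredient Delivery does enter here, but in cells that the plan itself describes as small.

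**Cell counts.** Fixing three factors (Meal yes, Cookware yes, Ingredient no) leaves 2^3 = 8 of 64 cells. So 65 / 8 = 8.125 families per cell, and 8.125 x 64 = 520 in all.

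**Precision.** The 95% half-width for two groups of n is 1.96 x sqrt(2/n), in SD units and without baseline adjustment. In the table, the Meal and Ingredient contrasts are averaged over the other factors.

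| Comparison | Cells | n per group | Half-width (SD) | If the 65 span 16 cells |
|---|---|---|---|---|
| One condition v control condition | 1 v 1 | 8.125 | 0.97 | 4.06 per group, 1.38 |
| Meal without Ingredient v Ingredient without Meal | 16 v 16 | 130 | 0.24 | 65 per group, 0.34 |
| Meal with Ingredient v Meal without Ingredient | 16 v 16 | 130 | 0.24 | 65 per group, 0.34 |
| Main effect of any factor | 32 v 32 | 260 | 0.17 | 130 per group, 0.24 |

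The last column takes 65 / 16 = 4.0625 per cell, 260 in all. It applies if N = 65 counts every combination with Meal and Cookware. That reading is less natural, because the plan says the 65 did not have Ingredient Delivery.

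The Meal x Ingredient interaction, as a difference of differences across four groups of 130, has half-width 1.96 x sqrt(4/130) = 0.34 SD. With groups of 65 it is 1.96 x sqrt(4/65) = 0.49 SD.

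Baseline adjustment at an assumed pre-post correlation of 0.5 multiplies each figure by sqrt(1 - 0.25) = 0.87. The 130 v 130 contrast then has about 0.21 SD.

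**Reading.** At 0.97 SD the condition-level interval extends further than any of the plan's cut-points (.30, .50, .80), so the labels cannot reliably rank the two delivery components. The factorial contrasts are about four times as precise: sqrt(130 / 8.125) = 4.

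**The case against.** A reader might infer that the chosen bundle is unsupported, or that Ingredient Delivery should have been kept. The documents do not support that. Escaping the negligible label does not make uptake equal. The plan ranks Meal Delivery and Cookware highest on feasibility and promise, which is a stated basis, and it places the participation figures in results that are not part of this document. Ingredient Delivery may have had lower uptake or smaller effects, and the feasibility criterion alone could then have separated the two.

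It would also be too strong to say that Ingredient Delivery was never examined, since the condition-level d values include it. Their weakness is imprecision, and it affects every component.

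A head-to-head test is not required to select components in a factorial screen. Main effects and interactions can serve, and a contrast confined to Cookware families would use only about 65 v 65 (0.34 SD).

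The group sizes are conditional. The plan mentions an automated random number generator but does not promise balance, and the 65 may be analysed families rather than all those randomised.

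Finally, Phase 2 randomises the bundle against usual care, so nothing here biases that comparison. Choosing partly on practical grounds is legitimate.

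All of this stands and limits the point. It does not supply the missing reason, and it does not make the described analyses able to answer the outcome question.

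**Conclusion.** The point holds as a gap in analysis and justification. The plan gives no reason specific to Ingredient Delivery, and its described analyses cannot reliably place that component against, or on top of, Meal Delivery. Whether the choice was right cannot be judged from these documents.

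Under equal allocation with the 65 in 8 cells, the unused randomised contrast has a half-width of about 0.24 SD, against about 0.97 SD for a single-condition comparison. If the 65 span 16 cells, the figures are about 0.34 and 1.38 SD. The ratio of four is the same under both readings, while the absolute figures depend on the unstated total.

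This is an inexpensive improvement worth making. The Phase 2 comparison and its sample size are untouched.

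**What to change.** In the Phase 1 Analytic Plan, add one baseline-adjusted factorial model for each primary outcome, fitted by randomised assignment over all families. It should give the main effects of Meal Delivery, Ingredient Delivery and Cookware and the Meal x Ingredient interaction, each with a 95% CI. With 0/1 coding of Meal (M) and Ingredient (I), the two contrasts of interest follow directly:

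- Meal without Ingredient v Ingredient without Meal: b_M - b_I.
- Ingredient added to Meal: b_I + b_MI.

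The averaged main effect of Meal is b_M + b_MI/2, and that of Ingredient is b_I + b_MI/2. Present these as estimates with intervals to guide selection, not as a further set of significance tests.

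Alongside, state the Phase 1 total and the numbers by assignment, report participation for all three components, and give the rule that excluded Ingredient Delivery. Describe Meal Delivery plus Cookware as preferred over Ingredient Delivery on outcomes only as far as these estimates support it. Otherwise say that Ingredient Delivery was dropped on participation or practical grounds.

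The cost is a few model terms on data already collected. The downside is that the intervals may be too wide to separate the two delivery components, which would soften the wording of the choice.
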